9.4.2 Operational Outcome Definition and Identification Process

All outcome variables will be provided by the obstetric HCP and/or pediatrician attending the birth. The HCP will be asked to describe any MCMs observed in the infant or fetus and will also be asked to report the gestational age and birth weight. These 2 variables will be used to calculate preterm birth (gestational age <37 weeks at birth) and LBW (birth weight <2500 g). A teratologist/geneticist will review all reported congenital anomalies and classify them using the CDC's MACDP system as specified in [Section 9.3.2](#). Additionally, the teratologist/geneticist will provide an opinion regarding the possible temporal association of the Menveo exposure to the development of observed defects. If additional information is needed to aid in classification or temporality assessment, the teratologist will request additional information using the targeted follow-up process outlined in [Section 9.4](#).

The SAC will meet periodically to review the data, discuss the MCM cases and their classification and temporality with the teratologist, and reach consensus on the coding and classification of MCMs and other primary endpoints.

9.4.3 Operational Variable(s) Definition

As is indicated in [Section 9.4](#), for women who self-enroll in the registry, maternal characteristics will be provided by the pregnant woman at registry enrollment. After the woman provides consent and medical release for her HCP(s) to provide data, the obstetric HCP will provide prenatal data (LMP, EDD, and CEDD), prenatal test data (test, date of test, and result), obstetrical history (previous pregnancies, live births, stillbirths, SABs, IABs, births with congenital malformations, and family history of congenital malformations), concomitant medical conditions, concomitant medications and vaccines, and alcohol, tobacco, and illicit drug use. At pregnancy outcome, the obstetric HCP will

provide pregnancy outcomes data (live birth, stillbirth, SAB, IAB, or ectopic or molar pregnancy) and infant outcome (gestational age, birth weight, and sex).

If HCPs provide de-identified data to the registry, they will provide required data on maternal characteristics, prenatal data, obstetrical data, and pregnancy outcome data.

9.4.4 Advisory Committee(s)

An SAC will be established to oversee the scientific affairs of the registry, including its ongoing monitoring. The SAC will comprise recognized experts in the fields of teratology, epidemiology, maternal and fetal medicine, and therapeutic areas from government, academia, private practice, and NVD. The SAC will meet prior to each registry report to review the accumulated body of data from the registry, including review and classification of reported MCMs, and to carry out any actions required, including review and interpretation of interim data analyses and reports and publications of registry data. The SAC may meet on ad hoc occasions if indicated. In addition to the above activities, the SAC will design and implement strategies to heighten awareness of the registry.

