3.5 Advisory Committee

The Scientific Advisory Committee (SAC) will provide an independent review of registry data and will include specialists from appropriate fields such as obstetrics, pediatrics, clinical research, genetics, epidemiology, and teratology from academic institutions, private practice, and/or government agencies.

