NVD did not study vaccination in pregnancy as one of the objectives of clinical studies before licensure. Pregnant women were excluded from enrollment, and the use of birth control, where appropriate, was an entry criterion. Despite this requirement, 43 women in studies V59P13, V59P17, and V59P18 were found to be pregnant during the 6-month follow-up period. Of these women, 37 were administered MenACWY. All 7 spontaneous abortions occurred among women vaccinated with MenACWY.

In addition to reports in clinical trials, NVD received reports of 10 additional instances of MenACWY exposure during pregnancy via passive post marketing safety surveillance. One pregnancy ended in spontaneous abortion (SAB) 52 days after vaccination with both MenACWY and a rabies vaccine. Two pregnancies ended in normal deliveries of healthy infants, and the outcomes of the remaining 7 pregnancies are unknown.

The Menveo Pregnancy Registry is established to meet a CBER post marketing commitment (PMC) and is designed to collect prospective data on pregnancy outcomes among women immunized with the Menveo vaccine within 28 days prior to conception or

at any time during pregnancy. The 28-day window prior to conception was established based on data from the Menveo product label (Menveo package insert, 2012). Effectiveness of the Menveo vaccine in subjects 11 through 55 years of age was evaluated in a randomized, controlled clinical study comparing the hSBA responses following 1 dose of Menveo, showing that 68%-75% subjects have seroresponse 28 days after vaccination with Menveo.

Menveo is not indicated in pregnancy. However, inadvertent pregnancy exposures are anticipated because the targeted age group for the vaccine includes young women of reproductive potential. The registry will add to the current clinical experience with Menveo by supplementing data from animal toxicology studies and human exposure data. Pregnancy data will be collected at registry enrollment, at the end of the second trimester of pregnancy, and at pregnancy outcome for both mother and infant. NVD sponsors the registry in consultation with specialists from appropriate fields such as obstetrics, pediatrics, clinical research, genetics, epidemiology, and teratology from academic institutions, private practice, and/or government agencies. These individuals constitute the Scientific Advisory Committee (SAC) and will provide an independent review of registry data.

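### The advisory committee is described as giving an independent review, but Section 9.4.4 seats sponsor members on it and nothing keeps them out of the consensus on major congenital malformations

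*Protocol*

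**What the plan says.** **Membership and role, as stated first.** Protocol Section 3.5 says: "The Scientific Advisory Committee (SAC) will provide an independent review of registry data". It draws the members "from academic institutions, private practice, and/or government agencies". The abstract (4.0) and Section 7.0 repeat this. Section 7.0 separates sponsor and committee: "NVD sponsors the registry in consultation with specialists from appropriate fields", and then, of those specialists, "These individuals constitute the Scientific Advisory Committee (SAC) and will provide an independent review of registry data". Section 12.2 has the SAC prepare manuscripts independently, while the sponsor may see them and comment before submission.

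**Membership, as stated later.** Section 9.4.4 describes the same committee as recognized experts in several fields and "therapeutic areas from government, academia, private practice, and NVD". It gives the committee the review and classification of reported MCMs and the interpretation of interim analyses.

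**What the committee decides.** Under Section 9.4.2 the SAC discusses the MCM cases, their classification and their temporality with the teratologist, and is to "reach consensus on the coding and classification of MCMs and other primary endpoints". A specialist acts before it: "A teratologist/geneticist will review all reported congenital anomalies and classify them using the CDC's MACDP system".

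**The concern.** Independent review is a property that the protocol claims for its committee, and a reader of the final report would rely on it. Sponsor members on the same committee, with no stated limit on their part, leave that claim without support in the text.

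MCM is the primary outcome where this has weight, because classifying it calls for judgement. Section 9.3.2 asks, for example, whether a finding in an infant born before 36 weeks is due to prematurity, and whether a transient or biochemical condition might reflect an unrecognized malformation. Few MCMs are expected, so each decision counts for a lot in the estimated prevalence.

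**Working it through.** **1. The sections side by side.**

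| Section | Who sits on the SAC | Role |
|---|---|---|
| 3.5 | Academia, private practice and/or government | Independent review of registry data |
| 4.0, 7.0 | The outside specialists whom the sponsor consults; they make up the SAC | Independent review of registry data |
| 9.4.4 | Government, academia, private practice and the sponsor | MCM review and classification; interpretation of interim analyses |
| 9.4.2 | (the SAC) | Consensus on MCMs and the other primary endpoints |
| 12.2 | (the SAC) | Prepares manuscripts independently; the sponsor comments |

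Section 3.5 alone does not exclude the sponsor, because it says whom the committee will include. Sections 4.0 and 7.0 are firmer: the specialists consulted by the sponsor are the committee, which leaves the sponsor outside it. Section 9.4.4 puts the sponsor inside. All of these are current sections; none is amendment-log text. No section makes the sponsor's members observers or recuses them.

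**2. Which outcomes are open to judgement.** Section 9.4.2 calculates preterm birth (<37 weeks) and low birth weight (<2500 g) from the reported gestational age and birth weight. The consensus formally covers them, but little is left to decide. MCM is what remains.

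**3. How much one MCM decision could matter (illustration).**

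Inputs: 58 live births, background prevalence p0 = 2.54% and a 4.46-fold detectable ratio at 80% power (Section 9.5); one-sample binomial with one-sided Type I error of 5% (Section 9.6.2).

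- The plan's own figure first. The critical count is the smallest r with P(X ≥ r | 58, 0.0254) ≤ 0.05. P(X ≥ 4) = 0.0599 and P(X ≥ 5) = 0.0159, so r = 5. At p1 = 4.46 × 0.0254 = 0.1133, P(X ≥ 5) = 0.801. The stated 80% power reproduces.
- Expected MCMs at background: 58 × 0.0254 = 1.47.
- 5 of 58 (8.6%): one-sided p = 0.016; exact one-sided 95% lower limit 3.46%, above 2.54%.
- 4 of 58 (6.9%): one-sided p = 0.060; lower limit 2.39%, below 2.54%.

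Moving one case from 5 to 4 therefore changes whether the lower limit clears background.

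**4. How special that case is.** The change needs exactly 5 MCMs before the disputed decision.

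- At background: P(X = 5) = P(X ≥ 5) − P(X ≥ 6) = 0.0159 − 0.0035 = 0.0124, about 1.2%.
- At a 4.46-fold increase: 0.8008 − 0.6547 = 0.1461, about 14.6%.

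These are probabilities of standing at the boundary. They are not probabilities that a sponsor member would alter a classification, which the document gives no means to estimate.

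**The case against.** The case against making much of this is fair in several respects.

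- **Independence of classification is not claimed in so many words.** The protocol attaches the word to the SAC's review of registry data. This stands. Sections 9.4.2 and 9.4.4 do make MCM classification part of that review, so the claim reaches it by inference.
- **There is no sponsor vote in the text.** A reader might infer that sponsor members could vote a case out. The documents do not support that: they describe consensus after discussion with the teratologist and mention no vote. Under consensus, sponsor members could not impose a reclassification alone, though they could influence or withhold agreement.
- **There are safeguards.** A teratologist/geneticist classifies every reported anomaly first, and Section 9.3.2 fixes rules: surveillance-program criteria, two or more conditional defects counted as a case, prematurity-related findings excluded, chromosomal defects included. These narrow the room for judgement. They do not close it: the protocol does not say that the teratologist is independent of the sponsor, and the consensus lies with the SAC.
- **Lack of blinding is no fault of this text.** A reader might add that classification is never blind to exposure. Every registered pregnancy is exposed and the comparators are external, the protocol never claims blinding, and changing the committee would not supply it.
- **The 5-to-4 change is a worst case.** Sections 8.0 and 9.7.1 call the registry primarily descriptive, and no section makes five MCMs a signal. Any study of a rare outcome is this fragile, whoever sits on its committee.

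None of this removes the disagreement between 7.0 and 9.4.4 or supplies a limit on the sponsor members' role.

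**Conclusion.** The point holds in a limited form. The protocol claims an independent review by the SAC, and its own description of the committee in 9.4.4 does not secure it. The practical weight falls on MCM.

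A reader might go further and conclude that classification of all the primary endpoints is compromised. The documents do not support that: preterm birth and low birth weight are calculated from reported values, and sponsor membership shows a stated safeguard missing, not actual bias.

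The size can only be illustrated. With about 1.5 MCMs expected at background, one decision would change the reading only if the count stood at the boundary. That illustration assumes 58 live births, a 2.54% background rate and the one-sided exact 5% settings used for power. This is a low-severity point with an inexpensive remedy.

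**What to change.** Make the SAC membership agree across Sections 3.5, 4.0, 7.0 and 9.4.4. In 9.4.2 and 9.4.4, add that any sponsor representatives attend as observers and take no part in the consensus on MCM classification or temporality.

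Removing the sponsor from the membership in 9.4.4 would also reconcile the text. So would dropping the claim of independence and describing what the sponsor's members do, but that gives up the safeguard.

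The change takes a few sentences and needs no new staff, data or analysis. Its cost is that the sponsor gives up its say in that consensus; as observers, its representatives would still hear the discussion.

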9.5 Study Size

Currently the market share of Menveo is approximately 20%, with an annual absolute dose distribution of 1.8 million in 2012. It can be assumed that market shares will remain stable over the course of the 3-year duration of the study. The Advisory Committee on Immunization Practices (ACIP) recommends routine administration of a MenACWY vaccine for all persons aged 11 through 18 years. A single dose of vaccine should be administered at age 11 or 12 years, and a booster dose should be administered at age 16 years. It is roughly estimated that of all Menveo vaccinations, approximately 76% are provided to individuals less than 18 years of age ([Novartis Vaccines and Diagnostics, 2012](#)). Given the low rate of pregnancy in this age group, exposure during pregnancy at the recommended ages can be expected to occur infrequently. Likewise, vaccination among women of peak reproductive age (25-29 years) can also be expected to be rare ([Ventura, 2012](#)). In addition, willingness to participate and completion of follow-up in the pregnant adolescent population are expected to be very low. It is therefore anticipated that, per year, approximately 15 exposed women will be enrolled through the registry system and that approximately 60 supplemental identified exposures of Menveo in pregnancy can be expected from external sources.

The registry is expected to prospectively enroll approximately 100 women with exposure to Menveo 28 days prior to conception or during pregnancy over a 3-year period. Approximately 58% of these pregnancies can be expected to result in a live birth ([Ventura, 2012](#)). Given the patient population will be mainly adolescents, a high percentage of these pregnancies can be expected to be unintended, unwanted, and likely

to result in IAB. Therefore, it is anticipated that the registry will yield approximately 58 live births. It is expected that the vast majority (99%) of pregnancy exposures will occur within 28 days prior to conception or early in the first trimester (before pregnancy status is known). If exposures occur later in pregnancy, results will be stratified by trimester of exposure, acknowledging that the power of stratified analyses to detect statistically significant differences will be limited by the sample size of each subgroup.

The expected low frequency of Menveo exposure in pregnancy will limit the statistical power of this study. As noted below, there should be sufficient power to identify risks for relatively common outcomes such as preterm birth and LBW. However, there is less power to identify risks of rarer outcomes such as MCM.

According to the CDC MACDP, the prevalence rate of MCMs for mothers <25 years of age in the US is 2.54% ([Correa, 2007](#)). With a sample size of 58 first trimester exposed pregnancies resulting in a live birth, the study will have 80% power to detect a 4.46-fold increase in the prevalence rate of MCMs as compared with the CDC MACDP rate.

According to the CDC National Vital Statistics System (NVSS), the prevalence rate of preterm birth for mothers <25 years of age is 12.37% ([Martin, 2012](#)). With a sample size of approximately 58 exposed live births, the study will provide 80% power to detect a statistically significant 1.99-fold increase in the prevalence rate of preterm birth as compared with the CDC NVSS rate.

According to the CDC NVSS, the prevalence rate of LBW for mothers <25 years of age is 8.70% ([Martin, 2012](#)). With a sample size of 58 exposed live births, the study will provide 80% power to detect a statistically significant 2.40-fold increase in the prevalence rate of LBW as compared with the CDC NVSS rate.

The registry acknowledges the challenges of enrolling this number of exposed pregnancies and will carefully monitor enrollment trends and outcomes. This is an open registry with initiation of patient recruitment from the time of launch.

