9.7 Data Analysis

Registry Case Management and Disposition

Prospective Registry Reports

The registry will encourage prospective registration, which is defined as registration of a pregnancy exposure prior to knowledge or perceived knowledge of the pregnancy outcome (e.g., structural defect or genetic abnormality noted on a prenatal test). Those with no abnormalities identified on a prenatal test prior to enrollment will be considered prospective and included in the analysis. The rationale, potential bias, and analytic techniques to address any bias that may be introduced by this practice are addressed in [Section 9.7.4](#).

Data from HCP provider networks and HMOs that provide de-identified data on all exposed pregnancies in their network will fall into the category of prospective registry reports, as these networks/HMOs provide objective data on every pregnancy exposure in the network/HMO, both positive and negative outcomes. Thus, they avoid the reporting bias inherent in retrospective reporting only after a negative outcome has been noted.

Retrospective Registry Reports

Retrospective reports will also include subjects for whom the pregnancy outcome has already occurred or an abnormality has been identified on a diagnostic or screening prenatal test prior to enrollment. Retrospective reports can be biased toward the reporting of more unusual and severe cases and are less likely to be representative of the general population experience than reports reported prior to knowledge of outcome. Therefore, retrospective reports will not be included in the primary analysis and statistical calculation of risk. Retrospective reports with reported MCMs and/or spontaneous fetal losses will be reviewed to aid in detection of early signals and listed in registry reports. Retrospective reports will not be actively solicited by the registry and will not be captured in the registry database unless a congenital anomaly is reported.

Loss to Follow-Up

For a prospective report or pregnancy where follow-up information on the pregnancy outcome (live birth, fetal loss, etc.) is never obtained or is unavailable, the pregnancy will be considered lost to follow-up. Subjects lost prior to pregnancy outcome will be tallied in the registry reports but not included in the statistical analyses.

Duplicate Registry Reports

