With registry reports coming from multiple health care providers, health care provider networks, and HMOs, it is important to ensure that each case is counted only once ([NBDPN, 2004](#)). Identification of duplicate reports may be problematic for the anonymously reported de-identified cases where there is no specific identifying information. Reports received by the registry will be reviewed for possible duplicate reporting. On receipt of a registration form, the report will be compared with other reports made by the same reporter or compared with other data (such as age, LMP, EDD, and exposure information) to determine if the same report was received previously. If no duplication is identified, the report will be entered into the database. If a duplicate report is later identified through recall or the systematic check for duplicates, the case reported earliest or the one with the most complete data will be maintained as the valid case and updated with any data from the other report not already captured. The duplicate report will be flagged and designated as “Invalid”, with the reason being “duplicate report”.

Evaluable Registry Reports

An evaluable report is a subject with data submitted or confirmed by an HCP that contains at least the minimum criteria for a report and is not lost to follow-up. Prospectively reported evaluable subjects with known outcomes will be included in the primary analysis for the registry report. Evaluable retrospective reports will be summarized separately in the report. Patient-reported data without HCP confirmation will be summarized separately in the report.

Invalid Registry Reports

An invalid registry report is a report for which the minimum data elements are never obtained despite requests for the missing data. If the minimum data are not provided initially, the report will be considered to be pending until all attempts to resolve queries for missing data and requests for follow-up information are complete. If, after all attempts at follow-up are made, the minimum criteria are still not met, the report will be considered invalid due to insufficient information. Invalid reports will not be included in the registry analyses.

Analysis Population

The primary population for analysis will include prospective evaluable subjects exposed to Menveo that are not lost to follow-up (ie, subjects with appropriate outcome information that meet the minimum criteria for evaluation).

Exclusions for Analysis Purposes

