9.7.3 Statistical Methods

Overall and stratum-specific point estimates and 1-sided 95% confidence intervals will be calculated using the exact binomial distribution for prevalence rates of MCMs, preterm birth, and LBW among pregnant women exposed to Menveo and their live births. Most structural defects have their origins in the first trimester of pregnancy, the period of organogenesis. In addition to overall prevalence of MCM, the analysis of MCMs will be stratified by trimester of exposure to Menveo. The prevalence rate of combined MCMs reported to the registry will be calculated as a proportion with the number of MCMs as the numerator and the number of live births as the denominator, among women with first trimester exposure. Pregnancy losses with reported MCMs occurring at or after 20 weeks' gestation will be included in the numerator of the estimate of risk for MCMs to increase sensitivity and to allow comparison of outcomes with the CDC MACDP, which calculates rates by this convention. A secondary analysis will be conducted including pregnancy losses with reported MCMs occurring at less than 20 weeks' gestation in the calculation of risk. The prevalence rate of combined MCMs in exposed cases will be compared with that of the CDC MACDP ([Correa, 2007](#)).

Only cases meeting the CDC MACDP criteria for a defect or with 2 or more conditional defects will be included in the primary analysis. Single minor defects do not constitute a MCM according to the CDC MACDP classification; therefore, they will be listed in the report, but not included in the primary analysis.

The prevalence rate of preterm births and LBW will be calculated as proportions, with the number of live births as the denominator. These prevalence rates in exposed cases will be compared with those of the CDC NVSS ([Martin, 2012](#)). Because MCMs are often associated with preterm birth and LBW, infants with MCMs will be excluded from

analyses of these outcomes and will not be counted in the numerator or denominator when prevalence rates are determined.

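### The 80% power statements rest on 58 live births with complete follow-up, although the protocol expects very low completion and excludes lost pregnancies from analysis

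*Protocol*

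**What the plan says.** Section 9.5 expects about 100 women to be enrolled prospectively over three years, applies a live-birth fraction of 58%, and concludes that "it is anticipated that the registry will yield approximately 58 live births". All three power statements then use 58: a 4.46-fold increase for major congenital malformation (MCM), a 2.40-fold increase for low birth weight (LBW), and for preterm birth "With a sample size of approximately 58 exposed live births, the study will provide 80% power to detect a statistically significant 1.99-fold increase". The section sums up that "there should be sufficient power to identify risks for relatively common outcomes such as preterm birth and LBW". The Abstract repeats the figures.

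The same section also says that "willingness to participate and completion of follow-up in the pregnant adolescent population are expected to be very low", and describes the population as mainly adolescents.

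Section 9.7 sets out who is analysed. On loss to follow-up: "Subjects lost prior to pregnancy outcome will be tallied in the registry reports but not included in the statistical analyses". On reports that never meet the minimum data requirements: "Invalid reports will not be included in the registry analyses". For preterm birth and LBW, section 9.7.3 also removes infants with MCMs from the "analyses of these outcomes and will not be counted in the numerator or denominator when prevalence rates are determined".

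**The concern.** The step from 100 enrolled to 58 births has one factor, the share of pregnancies that end in live birth, which 9.5 explains by induced abortion. Loss to follow-up happens after enrolment and has no factor of its own. The power statements therefore describe a registry that follows every enrolled pregnancy to its outcome, which the protocol itself does not expect. Section 9.7.4 discusses loss only as a possible bias, not as a cut in the number analysed.

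In a descriptive registry meant to detect signals, the detectable ratios tell the regulator and the Scientific Advisory Committee how large an increase an unremarkable result can argue against. If they are quoted for more births than will be analysed, a null finding will look more reassuring than it is. This matters most for preterm birth and LBW, where the protocol says power should be sufficient.

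**Working it through.** **Inputs.** Section 9.6.2: one-sample binomial test, one-sided type I error 5%. Section 9.5: reference rates p0 of 2.54% (MCM), 12.37% (preterm) and 8.70% (LBW); ratios 4.46, 1.99 and 2.40; n = 0.58 × 100 = 58.

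**Formula.** The critical count r is the smallest count with P(X ≥ r | n, p0) ≤ 0.05. Power is P(X ≥ r | n, ratio × p0).

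**Reproducing the protocol's figures at n = 58**

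| Outcome | p0 | ratio × p0 | r | attained alpha | power |
|---|---|---|---|---|---|
| MCM | 2.54% | 11.33% | 5 | 0.0159 | 80.1% |
| Preterm | 12.37% | 24.62% | 12 | 0.0494 | 79.9% |
| LBW | 8.70% | 20.88% | 10 | 0.0270 | 79.8% |

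The ratios that give exactly 80% are 4.455, 1.991 and 2.405, so the stated ratios are right for 58 births. A one-sided normal approximation does not reproduce them (90.2%, 81.8%, 87.3%), so the exact test is the one used.

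**Same test and same ratios with fewer births.** The protocol gives no loss rate. The percentages below are assumptions, applied evenly so that the live-birth fraction stays at 58%; for example, 20% loss gives 58 × 0.80 = 46.4, taken as 46.

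| Live births analysed | assumed loss | MCM | Preterm | LBW |
|---|---|---|---|---|
| 57 | one birth | 78.8% | 77.9% | 77.9% |
| 52 | about 10% | 85.5% | 65.4% | 78.6% |
| 48 | about 17% | 80.8% | 66.2% | 69.7% |
| 47 | about 19% | 79.5% | 63.2% | 79.4% |
| 46 | about 20% | 78.0% | 60.0% | 77.3% |
| 41 | about 30% | 69.7% | 57.3% | 64.6% |
| 29 | 50% | 65.3% | 42.4% | 58.3% |

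Exact power is saw-toothed because r is a whole number. Over n = 10 to 57, preterm power never reaches 80%; its maximum is 77.9%, at 57. MCM reaches 80% only at n = 48 to 54, and LBW only at n = 53 to 55. All three are below 80% at 56 and 57, and at every n from 47 down to 10.

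**Detectable ratio at 80% power**

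| Live births | MCM | Preterm | LBW |
|---|---|---|---|
| 58 | 4.46 | 1.99 | 2.40 |
| 53 | 4.00 | 2.17 | 2.39 |
| 46 | 4.59 | 2.30 | 2.47 |
| 41 | 5.13 | 2.36 | 2.75 |
| 29 | 5.58 | 2.69 | 2.98 |

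**Removal of infants with MCMs.** At the reference rate, 58 × 0.0254 = 1.5 infants leave the preterm and LBW analyses even if nobody is lost. Averaging power over a Binomial(58, 0.0254) number removed gives 76.7% for preterm and 78.8% for LBW.

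**If only direct enrollees are lost.** Section 9.5 expects 15 per year, so 45 in three years. Loss of 20% of them leaves (100 − 9) × 0.58 = 53 births; loss of 50% leaves (100 − 22.5) × 0.58 = 45. Power (MCM, preterm, LBW) is 86.5%, 68.1% and 80.5% at 53, and 76.5%, 70.0% and 75.0% at 45.

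**The case against.** - **Preterm saw-tooth.** 58 is a local peak for preterm birth. Power is 72.4% at 59 births and 79.0% at 62, so part of the fall just below 58 comes from the discreteness of the test. The detectable ratio is only 2.03 at 57 and 2.06 at 56, so about a doubling remains a fair description for very small losses. This stands. It does not explain 65.4% at 52 births or 60.0% at 46.
- **Low follow-up already counted.** The sentence on low willingness and follow-up leads straight into the forecast of 15 enrolments per year. That may explain a low enrolment forecast, but the 58% is applied to women already enrolled, and nothing is deducted after that.
- **External reports may lose fewer.** Networks and HMOs are described as reporting every exposed pregnancy, so applying 20% to 50% loss to all 100 may be too harsh. This is fair, and the calculation restricted to direct enrollees allows for it; preterm power still falls to about 70% or below.
- **Spare exposures.** The protocol says that "approximately 60 supplemental identified exposures of Menveo in pregnancy can be expected from external sources". If that is per year, 75 × 3 = 225 exposures, or about 130 births, could absorb about 55% loss and still leave 58. But the target and every power statement use 100 enrolled.
- **Smaller items.** Invalid reports may never be counted among the 100, because the minimum criteria are conditions of enrolment. The removal of infants with MCMs is small, and multiple births, which are included, could offset it. Both are fair.
- **Descriptive purpose.** The registry does not set out to test hypotheses, and 9.5 admits limited power and difficult enrolment. No estimate or interval changes. The 80% figures are nevertheless stated without a condition on follow-up.

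**Conclusion.** The concern holds. The three ratios are computed correctly, but for a number of births that needs complete follow-up, contrary to what section 9.5 expects and to how section 9.7 defines the analysis. For preterm birth the 80% statement fails at every number of births from 57 down to 10. For MCM and LBW it holds at some lower numbers and fails at others, and from 47 births down none of the three reaches 80%. At an assumed 20% loss the preterm ratio is 2.30 instead of 1.99; at 50% it is 2.69.

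The conclusion rests on the exact one-sided 5% test, which reproduces the protocol's figures, on 100 enrolled as the planning number, and on loss levels that are assumed because the protocol gives none. It affects what the registry is said to be able to detect, not the validity of its estimates. It should be corrected.

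**What to change.** In section 9.5 and the Abstract:

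1. State an expected loss to follow-up, separately for direct enrollees and for network or HMO reports, and the evaluable live births that result.
2. Restate the three detectable ratios at that number; the rows for 53, 46, 41 and 29 births above can be used. Take the preterm and LBW number net of infants with MCMs.
3. Print the critical count and attained alpha beside each ratio. Otherwise a row such as 53 births, where MCM (4.00) and LBW (2.39) look slightly better than at 58, would suggest that losing births helps.
4. Tie the sentence on sufficient power for preterm birth and LBW to the restated figures.

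The cost is protocol wording. No extra enrolment and no change to the analysis are needed. The one downside is that the stated preterm ratio, and at most loss levels the MCM and LBW ratios, become less favourable.
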